6.4 Concomitant Therapy

Throughout the study, investigators may prescribe any concomitant medications or treatments deemed necessary to provide adequate supportive care except for those listed in [Section 6.7](#).

Concomitant therapies are to be collected in the CRF from the signing of the ICF through the EOS visit. For concomitant therapies affecting bone metabolism, collect therapy name, indication, dose, unit, frequency, start date, and stop date. For all other concomitant therapies, collect therapy name, indication, start date, and stop date.

6.5 Medical Devices

The PFS used in this study will be provided by Amgen. The PFS will be used for administration of IP for all subjects. Additional details for the PFS is to be provided in the IPIM.

Other medical devices (eg, syringes, sterile needles, alcohol prep pads), which are not considered test articles, may be used in the conduct of this study as part of standard care. These devices that are commercially available are not usually provided or reimbursed by Amgen (except, for example, if required by local regulation). The investigator will be responsible for obtaining supplies of these devices.

6.6 Product Complaints

A product complaint is any written, electronic or oral communication that alleges deficiencies related to the identity, quality, durability, reliability, safety, effectiveness, or performance of a drug(s) or device(s) after it is released for distribution to market or clinic by either Amgen or by distributors and partners for whom Amgen manufactures the material. Drugs or devices include romosozumab/placebo and PFS.

This includes any drug(s) or device(s) provisioned and/or repackaged /modified by Amgen. Drug(s) or device(s) includes IP. Any product complaint(s) associated with an

IP(s) or non-IP(s) or device(s) supplied by Amgen are to be reported according to the instructions provided in the IPIM.

6.7 Excluded Treatments, Medical Devices, and/or Procedures During Study Period

The following treatments are not permitted during the study:

- Strontium (including strontium ranelate and over-the-counter strontium preparations)
- Fluoride (for treatment of osteoporosis)
- Vitamin K and vitamin K analogs (for treatment of osteoporosis)
- Activated vitamin D (1,25-di(OH) vitamin D, or 1 (OH) vitamin D)
- Intravenous bisphosphonates
- Oral bisphosphonates (cumulative dosing regimens of ≤ 1 month are acceptable)
- Denosumab
- Teriparatide or any PTH analogs
- Systemic oral or transdermal estrogen (cumulative dosing regimens of ≤ 1 month are acceptable, vaginal preparations and estrogen creams will be allowed at any time)
- SERMs (cumulative dosing regimens of ≤ 1 month are acceptable)
- Calcitonin (cumulative dosing regimens of ≤ 1 month are acceptable)
- Tibolone
- Prolonged (ie, > 3 months) oral glucocorticoid therapy at a prednisone equivalent dose of ≥ 5.0 mg/day (tapering glucocorticoid courses of ≤ 1 month duration are permitted regardless of dose; inhaled or topical glucocorticoids are permitted)
- Any cathepsin K inhibitor, such as odanacatib (MK-0822):
- Hormonal ablation therapy
- Cinacalcet

If a subject discontinues IP and begins an approved alternative osteoporosis therapy, every effort should be made to have the subject continue participation in the study and complete all scheduled assessments (ie, withdrawal of partial consent, see [Section 8.1](#)).

7. STUDY PROCEDURES

Screening assessments and study procedures outlined in this section and in [Table 1](#) can only be performed after obtaining informed consent. Refer to the applicable supplemental laboratory manuals for detailed collection and handling procedures.

7.1 Schedule of Assessments

Table 1. Schedule of Assessments

Period	Screening		Treatment Period						Follow-up Period
	1	2	3	4	5	6	7	8/ET	9/EOS
Visit	1	2	3	4	5	6	7	8/ET	9/EOS
Day/Month	Within 35 days of Day 1	Day 1	Month 1 ± 7 days	Month 2 ± 7 days	Month 3 ± 7 days	Month 4 ± 7 days	Month 5 ± 7 days	Month 6 -7/+3 days	Month 9 -7/+3 days
General and safety assessments									
Informed consent	X								
Demographics	X								
Medical history	X								
Fracture history	X								
Medication history	X								
Smoking and ethanol use history	X								
Substance use history	X								
Instructions for daily vitamin D & calcium supplementation	X								
Physical examination	X							X	
Physical measurements	X							X	
Vital signs	X		X					X	
Concomitant medications	X	X	X	X	X	X	X	X	X
Record serious adverse events	X								X
Record adverse events		X							X
Record disease-related events		X							X
Laboratory Assessments									
Serum chemistry	X	X	X		X			X	
Hematology	X	X	X		X			X	
Serum protein electrophoresis	X								
Hepatitis B & Hepatitis C testing	X								
Serum 25 (OH) vitamin D	X	X							
iPTH		X	X		X			X	
Pharmacokinetics		X	X		X			X	
Anti-romosozumab antibody		X	X		X			X	X
Bone turnover markers		X	X		X			X	

Footnotes defined on next page of the table

Table 1. Schedule of Assessments

Period	Screening		Treatment Period						Follow-up Period
	1	2	3	4	5	6	7	8/ET	9/EOS
Visit	1	2	3	4	5	6	7	8/ET	9/EOS
Day/Month	Within 35 days of Day 1	Day 1	Month 1 ± 7 days	Month 2 ± 7 days	Month 3 ± 7 days	Month 4 ± 7 days	Month 5 ± 7 days	Month 6 -7/+3 days	Month 9 -7/+3 days
Imaging Assessments									
DXA scan - Lumbar spine	X							X	
DXA scan - Proximal femur	X							X	
IP Administration									
In-clinic IP injection ^a		X	X	X	X	X	X		
vitamin D loading dose ^b		X							

Page 2 of 2

DXA = dual-energy x-ray absorptiometry; EOS = end of study; ET = early termination; iPTH = Intact Parathyroid Hormone.

^a Must be the last procedure at each dosing visit.

^b Vitamin D loading dose of at least 50 000 to 60 000 IU, preferably by oral route is required for all subjects with a serum 25 (OH) vitamin D level of ≥ 20 ng/mL and ≤ 40 ng/mL at screening. Subjects with a serum 25 (OH) vitamin D level of > 40 ng/mL at screening may also receive the vitamin D loading dose at the principal investigator's discretion.

7.2 General Study Procedures

Study assessments and procedures will be performed only after written informed consent is obtained. During the study, every effort should be made to keep subjects on the study schedule of procedures.

The procedures performed at each study visit are outlined [Table 1](#).

Details regarding each type of procedure are provided in subsequent sub-sections. Refer to the applicable supplemental central laboratory, IVRS, IPIM, and study manuals for detailed collection and handling procedures.

IP administration must be the last procedure after all other study visit procedures have been completed at each applicable visit.

7.2.1 Screening Enrollment and/or Randomization

Informed consent must be obtained before completing any other screening procedure or discontinuation of standard therapy for any disallowed therapy. After signing the written ICF, site will register the subject in the IVRS and screen the subject in order to assess eligibility for participation. Screening procedures may be performed on multiple days but must be completed within the 35-day screening window. If a subject has not met all eligibility criteria at the end of the 35-day window, the subject will be registered as a screen fail. Subjects who screen fail only the serum 25 (OH) vitamin D eligibility criterion may be eligible for rescreening once as described in [Section 7.2.2](#).

The screening procedures to be completed are designated in the Schedule of Assessments ([Table 1](#)).

During the screening period, albumin-adjusted serum calcium levels may be retested once in case of an elevated albumin-adjusted serum calcium level within 1.1x ULN as assessed by the central laboratory. To enroll subjects after retesting of albumin-adjusted serum calcium levels, an eligible albumin-adjusted serum calcium level must be confirmed by the central laboratory, and the subject must be randomized within the original 35-day screening window. These subjects should not be screen failed.

A blood sample will be collected during the screening period for serum protein electrophoresis to assess possible diagnosis of multiple myeloma or related lymphoproliferative disorder; the analysis will be performed by the local laboratory. Electrophoresis results within 6 months prior to signing informed consent will be acceptable.

At screening, laboratory assessments will be conducted to determine hepatitis B and C status as follows:

- If hepatitis B and/or hepatitis C status is known to be positive by serology, no additional laboratory testing procedures are required
- If hepatitis B and/or hepatitis C status is not known to be positive by serology, the following laboratory testing is required:
 - Hepatitis B Surface Antigen (HepBsAg) and total hepatitis B core antibody (HepBcAb)
 - If results are HepBcAb positive and HepBsAg positive, no additional testing is necessary
 - If results are HepBcAb positive and HepBsAg negative, additional testing for Hepatitis B virus DNA by polymerase chain reaction (PCR) is necessary
 - Hepatitis C virus antibody
 - If results are hepatitis C virus antibody positive, additional testing for hepatitis C virus RNA by PCR is necessary.

7.2.2 Rescreening

Rescreening is permitted only once, and only for subjects who fail the serum 25 (OH) vitamin D eligibility criterion (ie, subjects with a serum 25 (OH) vitamin D level < 20 ng/mL). Subjects who fail any other eligibility criteria are not permitted to be rescreened. To initiate rescreening, subjects must first be registered as screen failed in IVRS and subsequently registered as rescreened. Subjects will retain the same subject identification number assigned at the original screening. Subjects not entered into IVRS as a rescreen will not be eligible for randomization. Rescreening date is defined as the date of IVRS entry, and a 35-day rescreening window will commence at this time. Subjects are not required to re consent for the rescreening period.

During the rescreening period, the subject should receive vitamin D repletion following a protocol defined by the principal investigator. A serum 25 (OH) vitamin D level \geq 20 ng/mL must be confirmed by the central laboratory before the subject can be randomized. While it is possible to repeat the serum 25 (OH) vitamin D test during the rescreening period, vitamin D eligibility must be confirmed by the central laboratory and the subject must be randomized within the 35-day rescreening window.

The following procedures are to be completed during the rescreening period as designated in the Schedule of Assessments ([Table 1](#)):

- Laboratory assessments (vitamin D only)
- Serious adverse event reporting

- Documentation of concomitant medications
- Registration in IVRS
- Randomization via IVRS

Any other procedures already performed during the screening period (eg, imaging assessments, or laboratory assessments other than vitamin D status) do not need to be repeated during the rescreening period.

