- 213 Current, uncontrolled hyper- or hypothyroidism, Uncontrolled hyperthyroidism is defined as thyroid stimulating hormone (TSH) and thyroxine (T4) outside the normal range. Uncontrolled hypothyroidism is defined as TSH > 10.
- 214 Current, uncontrolled hyperparathyroidism or history of hypoparathyroidism, per subject report or chart review. Uncontrolled hyperparathyroidism is defined as: parathyroid hormone (PTH) outside the normal range in subjects with concurrent hypercalcemia; or PTH values > 20% above the upper limit of normal (ULN) in normocalcemic subjects.
- 215 Current hyper- or hypocalcemia, defined as albumin-adjusted serum calcium outside the normal range, as assessed by the central laboratory. Albumin-adjusted serum calcium levels may be retested once in case of an elevated albumin-adjusted serum calcium level within 1.1 x the ULN as assessed by the central laboratory.
- 216 Subject previously has entered this study or has previously participated in a study with a sclerostin antibody product.
- 217 Malignancy within the last 5 years, except non-melanoma skin cancers, cervical or breast ductal carcinoma in situ.
- 218 Possible diagnosis of multiple myeloma or related lymphoproliferative disorder, as assessed by serum protein electrophoresis performed by the local laboratory (electrophoresis results within 6 months of signing consent will be acceptable).
- 221 Positive results for human immunodeficiency virus, per subject report or chart review.
- 222 Use of oral bisphosphonates:
- any dose received within 3 months prior to randomization
 - more than 1 month of cumulative use between 3 and 12 months prior to randomization
 - more than 3 years of cumulative use, unless last dose received \geq 5 years prior to randomization

- 223 Use of intravenous (IV) bisphosphonates
 - Zoledronic acid:
 - any dose received within 3 years prior to randomization
 - more than 1 dose received within 5 years prior to randomization
 - IV ibandronate, IV pamidronate, or IV alendronate:
 - any dose received within 12 months prior to randomization
 - more than 3 years of cumulative use, unless last dose received \geq 5 years prior to randomization
- 224 Use of teriparatide or any PTH analogs:
 - any dose received within 3 months prior to randomization
 - more than 1 month of cumulative use between 3 and 12 months prior to randomization
- 225 Use of strontium ranelate, or fluoride (for osteoporosis):

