7.3.13.1 Screening Bone Mineral Density Assessment

To determine eligibility based on BMD T-score, lumbar spine and proximal femur DXA scans will be analyzed by the central imaging vendor.

For screening purposes, DXA scans of the lumbar spine and proximal femur taken up to 35 days prior to the beginning of the screening period may be used if all of the following criteria are met:

- Images were obtained as part of the routine standard of care, or following appropriate informed consent procedures
- Images were obtained by a trained technician, using the parameters specified by the central imaging vendor for this study (refer to the appropriate imaging manuals provided by the central imaging vendor)
- DXA images were obtained using the same DXA scanner that will be used for this study

To be eligible for the study, subjects must have at least 2 evaluable lumbar vertebrae and at least 1 evaluable proximal femur (as determined by the principal investigator or designee).

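### Rescreening repeats only vitamin D and has no time limit, so the calcium exclusion can rest on a value drawn before repletion and 73 or more days old at first dose

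*Protocol*

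**What the plan says.** **Screening.** Protocol Section 7.2.1 says that screening procedures "must be completed within the 35-day screening window". If criteria are still unmet "at the end of the 35-day window, the subject will be registered as a screen fail". Table 1 heads the screening column "Within 35 days of Day 1", and Section 3.5.1 says that subjects should be randomized within 35 days of consent.

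**Rescreening.** Section 7.2.2 allows one rescreening, only for a 25(OH) vitamin D level below 20 ng/mL. The steps are that "subjects must first be registered as screen failed in IVRS and subsequently registered as rescreened", and then: "Rescreening date is defined as the date of IVRS entry, and a 35-day rescreening window will commence at this time". No maximum time separates the two registrations, and no new consent is needed. Repletion, by a scheme that the investigator defines, takes place during the rescreening period. Vitamin D is the only laboratory test listed for that period. Of other procedures already done, the section says: "eg, imaging assessments, or laboratory assessments other than vitamin D status) do not need to be repeated during the rescreening period".

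**Calcium.** Exclusion 215 reads: "Current hyper- or hypocalcemia, defined as albumin-adjusted serum calcium outside the normal range, as assessed by the central laboratory". It gives no maximum age for the sample.

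**DXA.** Section 7.3.13.1 adds that scans "taken up to 35 days prior to the beginning of the screening period may be used" if three conditions on consent, technique and scanner are met. Table 1 schedules no further scan until month 6. SAP Appendix 13.1.2 takes the last scan on or before Study Day 1 as baseline, with no limit on its age.

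**The concern.** The calcium criterion is about the present, yet for a rescreened woman the only value that the protocol makes a condition of entry was drawn while she was vitamin D deficient. Between that sample and the first dose she receives repletion as well as the daily calcium and vitamin D that all subjects start at screening. Her calcium may have moved in either direction, and no step checks it before she is randomized.

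The protocol treats the age of a calcium value as important elsewhere. Under Section 7.2.1, a woman whose mildly raised calcium is retested must have an eligible value confirmed and be randomized inside the original 35-day window. A woman who was deficient and then repleted has no comparable limit.

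The same rule lets the baseline DXA precede repletion. For such women the month 6 percent change spans more than the treatment period and includes any response to repletion. The timing statements in Section 3.5.1, Table 1, Section 7.2.2 and Section 7.3.13.1 also do not agree with one another.

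**Working it through.** **Inputs (Protocol).**
- Screening window: 35 days (7.2.1).
- Gap from screen failure to rescreening entry: *g* ≥ 0, no limit stated (7.2.2).
- Rescreening entry to randomization: up to 35 days (7.2.2).
- Randomization to first dose: up to 72 hours, 3 days (6.2.1.1).
- Pre-screening scan allowance: up to 35 days (7.3.13.1).
- Day 1 to the month 6 target: 183 − 1 = 182 days (SAP Appendix 13.1.2).

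**The plan's own figure.** The documents state no maximum age for either measurement. The nearest stated figure is power above 99% (Protocol 10.2). With 27 per arm after 10% dropout, the standard error is 3.9 × √(2/27) = 1.06 and 6.6 / 1.06 = 6.2. Power from the noncentral t is above 99.99%, and the same holds with 30 per arm. The figure reproduces.

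**Age at first dose, each window fully used.**
- Calcium, rescreened: 35 + *g* + 35 + 3 = 73 + *g* days.
- DXA within screening, rescreened: also 73 + *g* days.
- DXA before screening, rescreened: 35 + 73 + *g* = 108 + *g* days.
- Without rescreening: calcium 35 + 3 = 38 days; pre-screening DXA 35 + 35 + 3 = 73 days.
- If each window is read as ending at Day 1, so that the 3 days drop out, the rescreened values at *g* = 0 are 70 and 105 days.

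| Gap *g* (days; values above 0 are assumed) | Calcium age | Oldest DXA age | Longest scan-to-scan interval |
|---|---|---|---|
| 0 | 73 | 108 | 290 |
| 30 | 103 | 138 | 320 |
| 60 | 133 | 168 | 350 |
| 90 | 163 | 198 | 380 |

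The last column is 182 days plus the DXA age. At *g* = 0 it is 290/182 = 1.59 times the treatment interval. For a scan taken within screening it is 182 + 73 = 255 days, about 8.4 months.

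**Size of the endpoint effect.** The documents give no background rate of BMD change. Assume 0.5% to 2% per year. Then 108 days contribute 0.5 × 108/365 = 0.15 to 2 × 108/365 = 0.59 percentage points to one woman's change. Against the 35 days in Table 1 the excess is 73 days, or 0.10 to 0.40 points. As an extreme, let half of all subjects carry the full 0.59 points and half none. The SD becomes √(3.9² + (0.59/2)²) = 3.91, against 3.9 planned.

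**Does Day 1 chemistry close the calcium gap?** Table 1 schedules chemistry on Day 1, and Section 7.4 has all blood drawn before dosing. The sample goes to the central laboratory, and the first dose is the last procedure of the visit (Section 7.2). No text makes the result a condition of randomization or dosing.

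**The case against.** Section 7.2.2 is a deliberate choice to limit repeat procedures, and it is permissive: sites may repeat tests. The Day 1 sample is the SAP baseline for laboratory data, so safety shifts are not measured from an old value. Only results after Day 1 are withheld from sites (Section 7.4), panic calcium values are released even then, chemistry is repeated at month 1, and Section 6.2.2.3 covers calcium abnormalities on study. All of this stands. It narrows the exposure to entry and first dose on an outdated eligibility value; it does not remove it.

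The 108 days require several maxima at once, including an optional scan at its limit. That also stands.

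A reader might infer three stronger things that the documents do not support.
- *That month 6 change covers nine months or more in rescreened women generally.* Nine months is about 274 days, so the scan must be at least 274 − 182 = 92 days old at Day 1. A scan taken within screening does not reach that at zero gap, and nothing suggests that long gaps are expected.
- *That these women are especially prone to hypocalcemia.* It is an event of interest in SAP Section 10.7.1.1, but the documents do not show that calcium is likelier to fall than to rise after repletion.
- *That the treatment comparison is biased or loses power.* Randomization follows rescreening, so old baselines fall on both arms alike in expectation, and the effect on the SD is trivial.

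Section 7.3.13.1 can fairly be read as a stated exception to the Table 1 column. It is still not cross-referenced there.

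**Conclusion.** The point holds as a gap in eligibility and timing rules. For rescreened women, exclusion 215 can be applied to a calcium value that precedes repletion and is up to 73 days old at first dose, plus a gap without limit. The limit is 38 days for a woman screened once. The baseline DXA can be up to 108 days old plus the gap in the extreme case, and 73 days plus the gap for a scan taken within screening.

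The endpoint consequence is secondary. It mainly changes what the within-arm month 6 percent change means for rescreened women; the treatment difference is protected in expectation and power is unaffected in practice.

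These sums assume that each window is used in full. The number of rescreened women is not given, so the share affected is unknown. Section 3.5.1 and the Table 1 column, read literally, would bar any woman randomized more than 35 days after her consent, or dosed more than 35 days after screening, which Section 7.2.2 plainly allows. The passages must be reconciled.

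**What to change.** 1. In Section 7.2.2, add serum chemistry with albumin-adjusted calcium to the blood sample already drawn for the rescreening vitamin D test. If that test is repeated, use the sample that confirms vitamin D eligibility. Apply the existing exclusion 215 to the result before randomization. The eligibility calcium is then at most 35 + 3 = 38 days old at first dose whatever the gap, as for other subjects. State how the single-retest provision, now tied to the original window, works at rescreening.
2. Reconcile Section 3.5.1, Table 1, Section 7.2.2 and Section 7.3.13.1, so that one rule governs the time from screen failure to rescreening entry and one rule governs the age of the baseline DXA at Day 1. The documents do not point to a particular number for either; the sponsor has to choose and justify them.

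The cost is a short amendment, one chemistry panel per rescreened woman on an existing draw, and possibly a few more screen failures. The change does not by itself require a repeat DXA, so a baseline scan could still precede repletion; the age rule would bound how far.

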7.2.3 Treatment Period

Visits will occur per the Schedule of Assessments ([Table 1](#)) during the treatment period from day 1 through month 6. Romosozumab is to be administered as the last procedure of each applicable visit.

Day 1 is defined as the day the first dose of IP is administered. All on-study visits (ie, visits after day 1) are calculated from the day 1 visit. If a subject's visit is delayed, their subsequent visit date is not to be shifted, and is always to be calculated from the day 1 visit. Month is defined as a calendar month.

If a subject withdraws from the study early, all efforts should be made to complete and report the observations as thoroughly as possible up to the date of withdrawal. The procedures for the month 6/ET visit should be completed at the time of withdrawal ([Table 1](#)).

